6.4. Safety Endpoints

The following primary safety endpoints will be assessed throughout each subject's participation in the investigation:

- All cause and device-related mortality
- Aortic disruption
- Exit Site infection
- Internal PIL/Cuff infection
- Thromboembolism
- Device malfunction
- All protocol-defined adverse events

6.5. Statistical Methodology

The sample size for the European protocol (N= 50 patients) was calculated on the basis of preliminary discussions with the Scientific Advisors of Sunshine Heart, and predicted success and safety rates observed in the literature data. Consistent design, procedures and endpoints of this study, as compared with the US trial, may allow pooling of data and comparative analyses. Demographic and baseline data will be summarized using descriptive statistics, including %, mean, median, standard deviation, and 1st-3rd quartile, as appropriate. The performance and safety endpoints of the C-Pulse® System will be assessed by monitoring the patient clinical status, assessing the standard quality-of-life scores, and evaluating vital, cardiopulmonary, hematology, biochemistry and neurological parameters, cardiopulmonary test data during the visits within the follow-up period, as detailed in the Data Collection Summary shown in Table 8. Follow-up analysis will include both safety and performance analyses, at each of the defined intervals. Adverse event data will be summarized using descriptive statistics. These will include information concerning nature, severity and duration of all adverse events and their relationship to the different treatments. In addition, tables will be presented for the number of patients potentially available for follow-up and those actually followed. Reference rates for anticipated complications (adverse events), based on historical data on morbidity and mortality from previous device clinical experience, in similar populations and for analogous surgical procedures, are listed in the Literature Review. Overall mortality rate will be determined at the end of the study.

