Implantation procedure	
The C-Pulse Cuff and the Sense Lead are implanted through a chest incision and without the use of cardiopulmonary bypass. Only a small pericardiotomy is required, limiting the potential for bleeding and for post-operative adhesions. The ascending aorta is isolated and its circumference measured. The circumferential length is noted on the pre-marked wrap. The Cuff is passed around the aorta such that the inflating aspect of the Cuff is positioned on the outside curvature. The Cuff is then checked to fit the aorta conformably and that the circumferential marks are appropriate prior to securing of the wrap with sutures. Pre-loaded interrupted 'mattress' sutures are placed through the tail of the Cuff at the appropriate circumferential marks with the Cuff 'open', and such that the inflation chamber of the Cuff is always visualized. The sutures are then tied down and the wrap checked to be conformal to the aorta. The excess wrap fabric is trimmed off. A bipolar ECG Sense Lead is placed on the heart, most preferably the left ventricular free wall. The gas line of the Cuff is trimmed to length and it and the ECG Sense Lead are attached to the intra-corporeal "Y- connector" end of the Percutaneous Lead. The Percutaneous Lead is then tunneled beneath the rectus sheath, the extra-corporeal end of the Lead having a Patient Connector permanently attached.
 
Alternatively, the lines may be tunneled to an intermediary incision for connection, particularly if a less invasive surgical technique (sternal-sparing) is used. The Percutaneous Lead is designed to be exchanged or removed if required, the latter eliminating the exit site. If removal occurs, the Cuff and Sense Lead can remain within the thorax with the gas line of the Cuff and the connector of the Sense Lead capped off and accessible with minimal surgery in the subcutaneous tissue of the abdominal area. If the Cuff is infected, it should be removed.

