Performance Endpoints	
The following performance endpoints will be assessed during follow-up visits:
 
• Improvement in INTERMACS™ and/or NYHA functional class• Freedom from worsening heart failure resulting in hospitalization, LVAD implantation, or death• Explant for recovery of ventricular function or cardiac transplantation 
Secondary endpoints assessed at 6 and 12 months post implant include:
 
• Improvement in LVEF• Improvement in Quality of Life scores• Improvement in 6MWT
Safety Endpoints	
The following primary safety endpoints will be assessed throughout each subject's participation in the investigation:
 
• All cause and device-related mortality• Aortic disruption• Exit Site infection• Internal PIL/Cuff infection• Thromboembolism• Device malfunction• All protocol-defined adverse events
Data collection	
The study will aim to collect patient data while supported with C-Pulse therapy (i.e. the subjects will be censored from analysis if the device is permanently "off" unless due to signs of recovery). Data will be captured at the following time points: Baseline, procedure, discharge assessment, clinical follow-up at 6 weeks, 6 months, 12 months, 18 months, 2 years and yearly thereafter. Data from any other additional time points may be collected and analyzed if available.
 
Data from baseline and up to 5 years of follow-up will be captured in an electronic database. Hemodynamic performance and functional testing will be determined according to procedures based on standard center practices. Any protocol-defined adverse events, including adverse device effects and outcomes will be reported by the Investigator.

Sponsor	
Sunshine Heart Inc. [name] [name] USA

Sponsor Contacts	
[name], Director of Clinical Studies [contact] Email [contact] [name], European Medical Director [contact] email: [contact]

ABBREVIATIONS

ACC	American College of Cardiology
AE	Adverse Event
AHA	American Heart Association
CABG	Coronary artery bypass grafting
CCS	Canadian Cardiovascular Society
CEC	Clinical Events Committee
CHF	Congestive Heart Failure
CI	Cardiac Index
CIP	Clinical Investigation Plan
CO	Cardiac output
CPB	Cardiopulmonary Bypass
CRF	Case Report Form
CRT	Cardiac Resynchronization Therapy
CTS	Cardiothoracic Surgeon
DMC	Data Monitoring Committee
EAB	Extra Aortic Balloon
EC	Ethics Committee

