Observed rate of exit site infections in the C-Pulse® clinical study was 40%. However the risks associated with this type of infection are low. Normally the resolution of this type of infection is managed through use of antibiotics, antiseptics, exit site management and PIL stabilization. Since C-Pulse® is not blood contacting, the risk of sequelae, particularly sepsis, is significantly less than observed with LVADs, thus exit site infections with the C-Pulse® device are not as high a risk as in LVADs. There remains a risk of ascending infection – exit-site pain, tenderness or swelling over the subcutaneous flocking, etc., should be investigated and treated aggressively. The PIL is specifically designed as a modular component of the C-Pulse® System, such that if an infection is chronic the PIL can be removed and the infection easily treated with antibiotics.

Adoption of the requirement for a stabilization device and new infection management techniques and protocol will require the sites to treat the C-Pulse® PIL as critically as the VAD drivelines to facilitate minimizing infection. The anticipated rate of residual risk in the post-market experience following implementation of the mitigations is expected to be no greater

than 30%. This rate is acceptable since it is consistent with what is currently being experienced with other devices having a drive-line exit site.

The clinical benefit of the PIL and its design features (e.g. ease of accessibility, ability for the patient to temporarily disconnect, removability) continue to support that the benefit outweighs the residual risk.

2) Sternal wound infection

During the C-Pulse® clinical study, one patient experienced a sternal wound infection resulting from the surgical procedure. The outcome of the management of the sternal wound after several attempts for debridement and a sternal flap was an aortic disruption. The rate of this incident is low, observed at 5% (1/20).

The risks associated with this type of infection are high if not properly managed. Resolution of this type of infection is normally managed through use of antibiotics and sternal wound debridement and drainage. If the sternal wound infection progresses to include the sternal bone the Cuff should be explanted to avoid infection of the Device.

3) Pneumo-mediastinum Infection

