5.6. Schedule of Assessments

The study will aim to collect patient data while supported with C-Pulse therapy (i.e. the subjects will be censored from analysis if the device is permanently "off"). Data will be captured at the following time points: Baseline, procedure, discharge assessment, clinical follow-up at 6 weeks, 6 months, 12 months, 18 months, 2 years and yearly thereafter. Data from any other additional time points may be collected and analyzed if available.

The treatment procedure will be performed according to the instructions outlined in the current approved IFU. The data will be recorded from baseline and during a 5 year follow-up period following the enrollment. Treatments will be performed according to standard hospital practices. The clinical assessments will be done as per routine practice at the participating institutions.

The clinical variables of interest are presented in **Table 8** below. Hemodynamic performance and functional testing will be determined according to procedures based on standard center practices. Any protocol-defined adverse events, including adverse device effects and outcomes will be reported by the Investigator. All available variables of interest, that will be collected by the investigators, will also be recorded in the Study electronic CRFs.

Table 3 .Data Collection Summary.

	Pre-Implant (Baseline)	Implant	Pre-Discharge ²	6 week	6, 18 month	Annually ¹ Yr 1-5
PATIENT ELIGIBILITY	X					
GENERAL						
Demographic Data	X					
Medical History	X					
General Physical Exam	X	X	X	X	X	X
Concurrent Cardiac Meds	X	X	X	X	X	X
Weight (Height at enrollment)	X		X	X	X	X
Pregnancy test (if applicable)	X					
VITAL PARAMETERS						
Heart rate/rhythm	X		X	X	X	X
Blood pressure	X		X	X	X	X
Respiration rate	X		X	X	X	X
CARDIOPULMONARY³						
ECHO	X				X	X
6MWT	X			X	X	X
QUALITY OF LIFE						
INTERMACS™/NYHA Classification	X			X	X	X
KCCQ	X				X	X
HEMATOLOGY						
Hemoglobin	X		X		X	X
Hematocrit	X		X		X	X
Platelet count	X		X		X	X
White cell count	X		X		X	X
C-reactive Protein	X		X		X	X
BIOCHEMISTRY						
Serum sodium	X		X		X	X
Serum potassium	X		X		X	X
Serum creatinine	X		X		X	X
BUN	X		X		X	X
NTProBNP or BNP ⁴	X				X	X
Serum bilirubin	X		X		X	X
Serum ALT	X		X		X	X
Serum AST/GGT	X		X		X	X
IMPLANT DETAILS		X				
DEVICE LOG		X			X	X
DISCHARGE CHECKLIST			X			
ADVERSE EVENTS	X	X	X	X	X	X
DATA FROM THE FOLLOWING ITEMS WILL BE COLLECTED IF COMPLETED UPON PHYSICIAN REQUEST:						
MVO2	X					X
Right Heart Catheterization	X					X

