6.2. Enrollment

A patient population of up to 50 patients with moderate to severe heart failure refractory to optimal medical therapy, who are implanted with the C-Pulse System as clinically appropriate, will be enrolled into the Study. A maximum of 15 European centers will participate. Study data from additional geographies may be included.

Patients diagnosed with moderate to severe heart failure and who are treated at the participating centers are eligible for screening evaluation. The investigator(s) will obtain informed consent for study participation from each patient.

Patients eligible for the study must meet all the inclusion criteria and not meet the exclusion criteria (indications and contraindications based on device CE mark authorization and Instructions for Use). In addition, a screening process will be carried out the objective of selecting ideal candidates for the C-Pulse System (see Section 5.5). Patients suitability will be evaluated in agreement between the Investigator and Sponsor, based on the assessment of heart failure severity, concomitant cardiac disease, need for concomitant cardiac surgery, co-morbidity, life expectancy < 2 years, pregnancy and other conditions potentially interfering with the ability to manage the C-Pulse therapy.

After implantation of the C-Pulse System, patients will be followed up for 5 years to collect performance and safety data.

The estimated time course of the study is as follows:

First Patient In: May 2013

Last Patient In: Dec 2014

Last Patient Out: Dec 2019

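### Exit-site infection is a primary safety endpoint over up to 5 years, but section 6.5 names no estimator based on time at risk and device-off censoring ends risk at the wrong event

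*Combined protocol and SAP*

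**What the plan says.** Section 6.4 lists exit-site infection among the endpoints for which "primary safety endpoints will be assessed throughout each subject's participation in the investigation". Section 6.2 sets the horizon: "patients will be followed up for 5 years to collect performance and safety data".

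For analysis, section 6.5 states "Adverse event data will be summarized using descriptive statistics" and "Follow-up analysis will include both safety and performance analyses, at each of the defined intervals", and adds tables of patients due and actually followed. Section 6.6 refers to two-sided 95% confidence intervals.

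Section 5.6 states that "subjects will be censored from analysis if the device is permanently" off. The synopsis (Data collection) gives the same rule with an exception, "unless due to signs of recovery", that section 5.6 lacks.

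On the lead, the synopsis (Implantation procedure) says: "The Percutaneous Lead is designed to be exchanged or removed if required, the latter eliminating the exit site". Section 4.3 names lead removal as an option when an exit-site infection is chronic.

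Section 4.3 reports a premarket exit-site infection rate of 40% and says of the post-market rate: "The anticipated rate of residual risk in the post-market experience following implementation of the mitigations is expected to be no greater" than 30%. Neither figure carries a period in the available text. Section 4.1 gives confirming the premarket results as part of the study's purpose.

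**The concern.** An infection that can occur at any time while a lead crosses the skin needs a defined start, end and unit of risk time. The plan supplies head counts by visit but no cumulative incidence, no rate per patient-year and no definition of who is at risk.

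The one rule that touches risk time ends it at the wrong event. Switching the driver off does not close the exit site; removing the lead does. Under section 5.6, a patient whose driver is permanently off but whose lead remains is dropped from a safety analysis while still exposed. Under the synopsis, the same patient stays in if the reason was recovery. Two analysts could follow the text and report different results for a primary safety endpoint.

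A percentage taken over all follow-up would also rise with time on device and fall with early exits. At stake is how the result can be interpreted beside the premarket experience that the study is meant to confirm.

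**Working it through.** **Inputs from the protocol.** Premarket 40% and expected 30% (4.3); mean time on device 335 days (4.2, C-PULSE SYSTEM Benefits); premarket denominator 20, taken from the 1/20 given for another infection in 4.3; 50 patients (6.6); up to 5 years (6.2).

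**Assumptions.** The 30% refers to 335 days (the protocol does not link them). Hazard shapes and exit rates are illustrative. The protocol states no exposure-adjusted figure to reproduce; 40% of 20 is 8 patients.

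**Step 1: hazard shape, no exits.** T0 = 335/365.25 = 0.917 years. Constant hazard h = -ln(0.7)/0.917 = 0.389 per year; risk by t is 1 - exp(-h t). The Weibull with shape 0.5 has risk 1 - exp(-0.357 x sqrt(t/0.917)).

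| Hazard, all giving 30% at 335 days | 12 months | 5 years |
|---|---|---|
| No infections after day 335 | 30% | 30% |
| Weibull, shape 0.5 | 31% | 57% |
| Constant | 32% | 86% |

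**Step 2: exits at rate m per year, constant hazard.** Proportion infected before exit = h/(h+m) x (1 - exp(-(h+m)t)).

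| m | 12 months | 5 years |
|---|---|---|
| 0 | 32% | 86% |
| 0.3 | 28% | 55% |
| 1.0 | 21% | 28% |

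This formula is also the cumulative incidence with exit as a competing event, so that estimator does not remove the effect of exits. It has to be read beside a rate.

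**Step 3: does a rate over full follow-up solve it?** Rate to first infection = proportion infected / mean infection-free time, no exits.
- Constant hazard: 0.39 per patient-year over any window.
- Weibull, shape 0.5: with a = 0.357/sqrt(0.917) = 0.372, mean infection-free time is (2/a²) x [1 - (1 + a sqrt(t)) exp(-a sqrt(t))], which is 0.726 years to day 335 and 2.93 years to 5 years. Rates: 0.300/0.726 = 0.41 and 0.565/2.93 = 0.19.
- No infections after day 335 (constant hazard before): 0.300/0.771 = 0.39 to day 335; over 5 years, 0.300/(0.771 + 0.7 x 4.083) = 0.300/3.63 = 0.08.

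A rate is therefore comparable with premarket only over a matching early window.

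**Step 4: premarket rate in the same form.** 20 x 0.917 = 18.3 patient-years; 8/18.3 = 0.44 per patient-year, exact Poisson 95% CI 0.19 to 0.86. This assumes that the 335 days and the 40% cover the same 20 patients at the same data cut. Time after a first infection is in the denominator, so the first-infection rate may be higher.

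**Step 5: precision.** A result of 16/50 (32%) has exact 95% CI 19.5% to 46.7%, which covers both 30% and 40%.

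**Step 6: driver off, lead in.** The protocol does not say how many patients would be in this state or for how long, so no size can be given. The direction is clear: infections arising in that time go uncounted.

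**The case against.** The other side has several good points.

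- **Descriptive need not mean crude.** Kaplan-Meier curves and patient-year rates are descriptive, and censoring is time-to-event language. A reader might infer that the plan commits to crude percentages that cannot be read against 40% or 30%. The text does not say so; the accurate statement is that no estimator is named.
- **Confidence intervals are already there.** Section 6.6 refers to 95% intervals and to literature-based reference rates in a table missing from the available text. The contents list also shows a clinical results section, and 6.5 cites a Literature Review; neither is available. Any of these may give a period for the benchmarks. None of what is visible defines time at risk.
- **Twelve months is already a planned interval,** and hazard shape matters little there. No comparison of a 5-year figure with 40% or 30% is planned. Both points stand.
- **Infected patients need not vanish from the tables.** A reader might infer that infections recorded before device-off would be deleted, making results look better. Nothing calls for that: ordinary censoring keeps earlier events, section 7.3 allows data obtained before loss to follow-up to be used, and section 4.2 (Benefits) describes lead substitution for exit-site infection, which is not an exit. One sentence saying that such infections are kept is enough.
- **Dates are partly covered.** Section 6.5 requires event duration, 8.1 has events reported as they occur, and Table 3 schedules a device log. But 7.4 lists onset date only among items source documents may contain, late explant reports under 8.3.2 are best effort, and device-off and lead dates are not named.

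These points narrow the concern. They do not answer the mismatch between device-off and the end of risk, or the conflict between section 5.6 and the synopsis.

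**Conclusion.** The concern holds in a limited form and should be addressed. A primary safety endpoint has no defined time at risk, and its only censoring rule is stated two ways and stops at driver-off when exposure ends at lead removal. This goes beyond missing detail, because following section 5.6 as written removes patients who are still at risk.

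Under the assumptions shown, a 5-year figure for a device performing as expected could lie anywhere from 28% to 86%, depending on hazard shape and exits. At 12 months hazard shape moves it only from 30% to 32%, although exits at 0.3 or 1.0 per year would still lower 32% to 28% or 21%. The sizes rest on linking 30% to 335 days and on assumed hazards and exit rates; the dependence on exposure does not.

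A reader might go further and conclude that a formal comparison or the sample size is invalid. It is not: the 30% is an expectation in the risk section, and the plan sets no test against it or against 40%.

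**What to change.** In section 6.5, for all implanted patients:

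1. Report the cumulative incidence of first exit-site infection from implant at 12 months, or at the period the sponsor confirms for the 40%, with a 95% CI. Treat death and lead removal without replacement as competing events.
2. Keep patients at risk while a lead is in place, whether or not the driver is running. A lead exchange is not an exit. Keep infections that occurred before any exit.
3. State that this replaces the device-off censoring of section 5.6 and the synopsis for this endpoint.
4. Report infections per patient-year with the lead in place by period, for example 0 to 12 months and after 12 months. Compare with the premarket rate only over the matching early window, not over full follow-up.
5. Record infection onset, device-off, lead-exchange and lead-removal dates in the e-CRF.

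The cost is a few sentences and four date fields, with no extra visits or patients. The dates are best collected prospectively. Downsides: infections after 12 months appear only in the later-period rate; cumulative incidence falls when exits are frequent, so it must be read with the rate; and with 50 patients neither is likely to separate 30% from 40%.

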7.3. Patients Lost to Follow-up

Patients that refuse to make their data available at a certain time point will be considered "lost to follow-up". The data that has been obtained from a patient that was subsequently lost to follow-up may still be used in any subsequent analysis.

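### The mortality rate has no defined estimator, and the device-off censoring rule, applied as written, removes later deaths from an all-cause endpoint

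*Combined protocol and SAP*

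**What the plan says.** Section 6.4 lists "All cause and device-related mortality" first among the primary safety endpoints and sets the window: "The following primary safety endpoints will be assessed throughout each subject's participation in the investigation". The only sentence in section 6.5 that names mortality as an analysis is "Overall mortality rate will be determined at the end of the study". The same section adds "Follow-up analysis will include both safety and performance analyses, at each of the defined intervals" and promises that "tables will be presented for the number of patients potentially available for follow-up and those actually followed". It names no Kaplan-Meier, person-time or competing-risk method.

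The censoring rule sits elsewhere. Section 5.6 states that "the subjects will be censored from analysis if the device is permanently" off, with no exception. The data-collection row of the synopsis gives the same rule but adds "unless due to signs of recovery".

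On other exits, section 9.6 lets patients withdraw at any time. Section 7.3 classes those who refuse to provide data as lost to follow-up and says "The data that has been obtained from a patient that was subsequently lost to follow-up may still be used in any subsequent analysis". Sections 6.2 and 7.9 foresee 5 years of follow-up for every patient. The synopsis and sections 4.1 and 5.2 allow consent to be obtained after the procedure.

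**The concern.** The plan uses the word censoring but names no estimator that can use censored observations. Neither statement of the device-off rule says whether a death after that point still counts toward all-cause mortality. Taken literally, it does not. Permanent device-off may well be related to prognosis: it can follow recovery, infection, progression to LVAD, or transplant. Removing what happens afterwards is therefore unlikely to be neutral.

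At stake is the main safety figure of a 50-patient post-market study. Section 6.5 foresees pooling and comparison with the US trial, and section 6.6 claims adequate precision for inference with 95% confidence intervals. With the rate undefined, an analyst could choose among materially different figures after seeing the data.

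**Working it through.** **The plan's own figure.** The available text gives no expected mortality, hazard or loss rate, so there is no mortality figure to reproduce. The sample size is 50 (section 6.6). Every rate below is an assumption.

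**Does device-off happen?** Section 4.2 reports that two premarket patients were weaned within one year. If the denominator is the 20 implied by the 1/20 figures in section 4.3 (an assumption), that is 2/20 = 10% in year one from weaning alone. Section 5.6 would censor such patients; the synopsis would not.

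**Illustration 1: equal hazards.** Let h be the death hazard and c the hazard of leaving analysis for any reason. Both are constant over 5 years, and leaving does not alter the risk of death.

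- True 5-year mortality = 1 − exp(−5h)
- Crude (observed deaths / all enrolled) = h/(h+c) × [1 − exp(−5(h+c))]
- Censored patients dropped = crude / (1 − proportion censored). With h = c, the proportion censored equals the crude figure.

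| h = c per year | True | Crude | Censored dropped |
|---|---|---|---|
| 0.05 | 1 − exp(−0.25) = 22.1% | 0.5 × (1 − exp(−0.5)) = 19.7% | 0.197/0.803 = 24.5% |
| 0.10 | 1 − exp(−0.5) = 39.3% | 0.5 × (1 − exp(−1.0)) = 31.6% | 0.316/0.684 = 46.2% |
| 0.15 | 1 − exp(−0.75) = 52.8% | 0.5 × (1 − exp(−1.5)) = 38.8% | 0.388/0.612 = 63.5% |

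**Illustration 2: risk changes after device-off.** Assume a 50% 5-year on-device death risk and a 30% 5-year device-off risk. Then h = −ln(0.5)/5 = 0.1386 and c = −ln(0.7)/5 = 0.0713.

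- Crude = 0.1386/0.2100 × (1 − 0.5 × 0.7) = 0.660 × 0.65 = 42.9%, or 21.5 deaths in 50.
- Proportion censored = 0.340 × 0.65 = 22.1%, so dropping them gives 0.429/0.779 = 55.1%.
- Kaplan-Meier censored at device-off is expected to give 50.0%.
- True 5-year mortality, counting deaths after device-off at 0.5, 1 or 2 times the on-device hazard, is 46.9%, 50.0% or 54.4%.

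Over assumed death risks of 30% to 70%, device-off risks of 10% to 70% and hazard ratios after device-off of 0.5 to 2, the crude proportion is below the truth by 0.7 to 34.7 points. Dropping censored patients gives between no difference and an excess of 26 points. Kaplan-Meier censored at device-off is too high at a ratio of 0.5, correct at 1 and too low at 2. With no censoring, all the figures agree.

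**The case against.** The strongest reply is that the plan leaves the rate undefined but does not commit to a wrong one. A reader might infer that it will report deaths over 50 and so must understate mortality. The documents do not say that. Being censored from analysis could equally mean time-to-event censoring or removal from the denominator, and removal generally overstates. The direction is conditional.

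A reader might also infer that the bias persists however the device-off rule is settled. That goes too far. Nothing states that LVAD or transplant ends participation; such patients would leave analysis only because the device is then off. If deaths are counted regardless of device status, only withdrawal and refusal can bias a crude 5-year proportion, and their frequency is not given. Nor is the 5-year length itself a cause: last patient in is December 2014 and last out December 2019, so each patient has a potential 5 years.

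Two further stronger readings fail. The end-of-study rate need not be the only mortality figure, because safety is also analysed at each interval, although that sentence names neither mortality nor a method. And one cannot say that the rate would be incomparable with the reference rates, because those are in a Literature Review outside these documents and their time basis is unknown.

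The planned tables of patients available and followed would make incomplete follow-up visible, but they do not correct for it. At the lowest hazards the gap is about 2 points, small beside a Wald 95% margin of about ±11 points for 10 deaths in 50.

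What remains is a stated rule that, read literally, excludes deaths from an all-cause endpoint, and no estimator for patients who leave early.

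**Conclusion.** The point holds in this limited form and should be corrected before analysis. The mortality estimator is undefined, and the device-off rule as written is incompatible with an all-cause endpoint. Bias is downward for on-device deaths over all enrolled, generally upward if censored patients are dropped, and of either sign for Kaplan-Meier censored at device-off. In the equal-hazard illustrations the crude shortfall is about 2, 8 and 14 points. These sizes rest on assumed constant hazards and on leaving being unrelated to prognosis; they show that the choice of estimator matters and do not predict this study's error.

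**What to change.** - State that the device-off censoring rule does not apply to all-cause mortality, and reconcile the synopsis with section 5.6 on the recovery exception.
- Estimate all-cause mortality from implant by Kaplan-Meier in all implanted enrolled patients regardless of device status. Censor only at withdrawal, loss to follow-up or 5 years. Give 95% confidence intervals and numbers at risk at 6, 12 and 24 months and 5 years.
- Enter patients consented after the procedure into the risk set at their consent date. They had to survive to consent, so counting them from implant without delayed entry would itself bias mortality downward.
- Report device-related death by cumulative incidence with other death as a competing event. Report on-device results separately, with device-off, LVAD and transplant as competing events.

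Kaplan-Meier still assumes that the remaining withdrawal and loss are uninformative; the planned follow-up tables help to judge that. The analysis itself is standard output. The real cost is in data collection: section 5.6 aims to collect data during support, so vital status would have to be obtained after device-off, up to the 5 years already planned. The resulting figure may also be less favourable.
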